1.2 Important Identified Risks, Potential Risks, and Missing Information

Term	Definition
Important identified risk	
Hypoglycemia	Adverse events of the following PT Codes (term) are defined as hypoglycemia. 10020994(Hypoglycaemia neonatal) 10040576(Shock hypoglycaemic) 10021000(Hypoglycaemic coma) 10020993(Hypoglycaemia) 10065981(Hypoglycaemic unconsciousness) 10021002(Hypoglycaemic encephalopathy) 10048803(Hypoglycaemic seizure) 10020997(Hypoglycaemia unawareness) 10077216(Hyperinsulinaemic hypoglycaemia) 10059035(Postprandial hypoglycaemia)
Acute pancreatitis	Adverse events of the SMQ Code 20000022 (acute pancreatitis (SMQ) narrow scope are defined as acute pancreatitis.
Hepatic impairment / jaundice	Adverse events of the SMQ Code 20000005 (hepatic disorders (SMQ) broad) are defined as hepatic impairment / jaundice.
Skin disorder including oculomucocutaneous syndrome (Stevens-Johnson syndrome) / erythema multiforme	Adverse events of the SMQ Code 20000020 (severe skin adverse reactions (SMQ) narrow) are defined as skin disorder including oculomucocutaneous syndrome (Stevens-Johnson syndrome) / erythema multiforme.
Rhabdomyolysis	Adverse events of the SMQ Code 20000002 (rhabdomyolysis/myopathy (SMQ) narrow) are defined as rhabdomyolysis.
Intestinal obstruction	Adverse events of the SMQ Code 20000105 (gastrointestinal obstruction (SMQ) narrow) or the HLGT Code 10018008 (gastrointestinal stenosis and obstruction) or HLT Code 10052736 (non-mechanical ileus) are defined as intestinal obstruction.
Interstitial pneumonia	Adverse events of the SMQ Code 20000042 (interstitial lung disease (SMQ) narrow) are defined as interstitial pneumonia.
Angioedema	Adverse events of the SMQ Code 20000024 (angioedema (SMQ) narrow) are defined as angioedema.
Important potential risk	
Infection	Adverse events of SOC Code 10021881(infections and infestations) are defined as infection.
Malignant tumor	Adverse events of the SOC Code 10029104 (neoplasms benign, malignant and unspecified (incl cysts and polyps)) are defined as malignant tumor.

Malignant tumor (narrow sense)	Adverse events of the SMQ Code 20000194 (malignant tumors (SMQ) narrow) are defined as malignant tumor (narrow sense).
Pemphigoid	Adverse events of the PT Code 10067776 (ocular pemphigoid) or 10034277 (pemphigoid) are defined as pemphigoid.

Term	Definition
Important missing information	
Cardiovascular system risk	
Adverse events of the SMQ Code 20000047 (myocardial infarction (SMQ) broad) or SMQ Code 20000061 (central nervous system haemorrhages and cerebrovascular conditions (SMQ) broad) are defined as cardiovascular system risk.
 
“Central nervous system haemorrhage and cerebrovascular conditions (SMQ) broad” includes the following SMQ classes.
 
 ➤ 20000166(Conditions associated with central nervous system haemorrhages and cerebrovascular accidents (SMQ) broad) ➤ 20000064(Cerebrovascular disorder haemorrhagic (SMQ) broad) ➤ 20000063(Cerebrovascular disease ischaemic (SMQ) broad)

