**Table 1 Definition of adverse event**

An adverse event (AE) is defined as any unfavorable event that develops after a pharmaceutical product is administered and which does not necessarily have a causal relationship with treatment. An adverse event can therefore be any unfavorable and unintended sign (including an abnormal laboratory finding, for example), symptom, or disease temporally associated with the use of a medicinal product, whether or not considered related to the medicinal product.
 
The following events will be handled as adverse events:
 
 
• Symptoms present in infants breastfed by a Nesina taking mother
 
• Symptoms present in children who received the relevant drug
 
• Symptoms due to occupational exposure to the relevant drug
 
• Symptoms due to counterfeit medications of the legitimate medicinal products manufactured by Takeda
 
• Unfavorable symptoms present in the patient who received the relevant drug, known by a lawsuit or other legal actions
 

---

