Patients with diabetic neuropathy	Patients with complication of PT Code 10012645 (diabetic autonomic neuropathy), 10012676 (diabetic mononeuropathy), or 10012680 (diabetic

Term	Definition
	neuropathy).
Patients with concurrent hypertension	Patients with concurrent disease of the Standardised MedDRA Query (hereinafter SMQ) Code 20000147 (hypertension (SMQ) narrow).
Patients with concurrent dyslipidemia	Patients with concurrent disease of the SMQ Code 20000026 (dyslipidaemia (SMQ) narrow).
Patients with concurrent hyperuricemia	Patients with concurrent disease of the PT code meeting the Takeda MedDRA Query 20.1 (hereinafter, TMQ 20.1) (blood uric acid increased).
Patients with concurrent liver disorder	Patients with concurrent disease of the SMQ Code 20000005 (hepatic disorders (narrow).
Patients with concurrent hepatic steatosis	Patients with concurrent disease of the PT Code 10019708 (hepatic steatosis).
Patients with concurrent alcoholic hepatitis	Patients with concurrent disease of the PT Code 10019728 (hepatitis alcoholic).
Patients with concurrent chronic hepatitis	Patients with concurrent disease of the PT Code 10008909 (chronic hepatitis).
Patients with concurrent hepatic cirrhosis	Patients with concurrent disease of the PT Code 10019641 (hepatic cirrhosis).
Patients with concurrent renal disorder	Patients with concurrent disease of the TMQ 20.1 (renal disease).
Patients with concurrent nephrotic syndrome	Patients with concurrent disease of the PT Code 10029164 (nephrotic syndrome).
Patients with concurrent glomerulonephritis	Patients with concurrent disease of the PT Code 10018364 (glomerulonephritis) or the PT Code 10018367 (glomerulonephritis chronic).
Patients with concurrent chronic renal failure	Patients with concurrent disease of the PT Code 10064848 (chronic kidney disease) or the PT Code 10038435 (renal failure).
Patients with concurrent heart disease	Patients with concurrent disease of the SOC Code 10007541 (cardiac disorders).
Patients with concurrent cardiac failure	Patients with concurrent disease of the SMQ Code 20000004 (cardiac failure (SMQ) narrow).
Patients with concurrent myocardial infarction	Patients with concurrent disease of the SMQ Code 20000047 (myocardial infarction (SMQ) narrow).

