5.0 Safety Tabulation and Analysis

5.1 Occurrence of adverse events and adverse drug reactions / infections

5.1.1 Occurrence of adverse events

(1) Patients to be tabulated and analyzed

Safety Analysis Set

(2) Details of tabulation and analysis

The following will be tabulated for adverse events.

Total patients and patients who are taking concomitant insulin preparation, rapid-acting insulin secretagogues, SGLT-2 inhibitors, or other drugs will be tabulated.

Parameter	Details of analysis
Number of patients with adverse events	Number of patients who experienced adverse events.
Number of adverse events	Number of adverse events. Count as an event if the same adverse event (LLT) occur multiple times in a patient. Count as different events for different LLTs even if they have the same PT.
Percent of patients with adverse events	Described in Section 1.1.
Type of adverse events	Will be broadly divided into the SOCs and tabulated by PT in the SOCs. In case of the laboratory test-related events, type of adverse events will be broadly divided into the SOCs and HLGTs for tabulation by PT. For the SOCs, the number of patients with adverse events and percent of patients with events will be described in the order of SOCs agreed internationally. For the PTs, the number of adverse events and percent of events will be described in the ascending order of PT codes. Count as an event if the same adverse event (LLT) occur multiple times in a patient. Count as different events for different LLTs even if they have the same PT.

(3) Number of tables and figures

Table 5.1.1-1

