5.1.3 Important Identified Risks, Important Potential Risks, and Important Missing Information

(1) Patients to be tabulated and analyzed

Safety Analysis Set

(2) Details of tabulation and analysis

The following will be tabulated for important identified risks, important potential risks, and important missing information (described in Section 1.2).

Total patients and patients who are taking concomitant insulin preparation, rapid-acting insulin secretagogues, SGLT-2 inhibitors, or other drugs will be tabulated.

Parameter	Details of tabulation and analysis
-----------	------------------------------------

Parameter	Details of tabulation and analysis
Number of patients with adverse events (or adverse drug reactions, etc.)	Number of patients who experienced adverse events (or adverse drug reactions, etc.) with important identified risks, important potential risks, and important missing information.
Number of adverse events (or adverse drug reactions, etc.)	Number of adverse events (or adverse drug reactions, etc.) with important identified risks, important potential risks, and important missing information. Count as an event if the same adverse event (or adverse drug reaction, etc.) (LLT) occur multiple times in a patient. Count as different events for different LLTs even if they have the same PT.
Percent of patients with adverse events (or adverse drug reactions, etc.)	Described in Section 1.1.
Type of adverse events (or adverse drug reactions, etc.)	Will be broadly divided into the important identified risks, important potential risks, and important missing information and tabulated by PT in them. For the PTs, the number of adverse events (or adverse drug reactions, etc.) and percent of adverse events (or adverse drug reactions, etc.) will be described in the ascending order of PT codes. Count as an event if the same adverse event (or adverse drug reaction, etc.) (LLT) occur multiple times in a patient. Count as different events for different LLTs even though they have the same PT.

(3) Number of tables and figures

Tables 5.1.3-1 and 5.1.3-2

5.2 Occurrence of Adverse Events and Adverse Drug Reactions / Infections in the Not Safety Analysis

Set

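### SAP 1.2 defines hypoglycaemia by ten condition terms and no laboratory term, so a low glucose coded as a laboratory finding would fall outside the hypoglycaemia patient counts in Tables 5.1.3-1 and 5.1.3-2

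*SAP*

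**What the plan says.** SAP 1.2 lists hypoglycaemia first among the important identified risks and fixes its content by enumeration: "Adverse events of the following PT Codes (term) are defined as hypoglycemia". The list opens with "10020994(Hypoglycaemia neonatal) 10040576(Shock hypoglycaemic) 10021000(Hypoglycaemic coma) 10020993(Hypoglycaemia" and closes with "10077216(Hyperinsulinaemic hypoglycaemia) 10059035(Postprandial hypoglycaemia". No standardised query, higher-level grouping or laboratory criterion is added. The same ten codes stand in all three SAP versions in the file.

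Protocol Table 1 defines an adverse event to include "any unfavorable and unintended sign (including an abnormal laboratory finding, for example), symptom, or disease". A low glucose value can therefore be reported as an event in its own right.

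SAP 5.1.1 plans for such reports: "In case of the laboratory test-related events, type of adverse events will be broadly divided into the SOCs and HLGTs for tabulation by PT".

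SAP 5.1.3 builds the risk tables from the Section 1.2 definitions. Of the event types it says: "Will be broadly divided into the important identified risks, important potential risks, and important missing information and tabulated by PT in them".

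**The concern.** The survey follows patients who take Nesina on top of insulin, a rapid-acting secretagogue or a similar agent. Hypoglycaemia is the risk that many readers will look up first, and they will look in Tables 5.1.3-1 and 5.1.3-2. If one physician writes a diagnosis of hypoglycaemia and another writes a low glucose result, and the coder follows the wording, the first patient enters the hypoglycaemia row and the second does not.

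At stake is how the patient count is read. A reader will take it to cover every hypoglycaemia-type event reported, whereas by construction it covers only those coded to a condition term. The SAP neither states this limit nor gives a way to see how much it matters.

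**Working it through.** The documents give no event rate, precision target or sample-size figure for hypoglycaemia, so there is no stated number to reproduce. The check traces one report through the plan and then adds an illustration.

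**1. The list (SAP 1.2).** Counting the codes gives 10, all distinct. Searching the ten terms for words that mark a test result (glucose, blood, decreased, test) finds 0.

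**2. The path of a low glucose reported as a laboratory finding.**
- It qualifies as an adverse event under Protocol Table 1.
- If it is coded to a laboratory preferred term, SAP 5.1.1 places it in a laboratory SOC/HLGT block.
- That term is not among the ten, so under SAP 5.1.3 the event cannot enter the hypoglycaemia rows.

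The coding step is conditional. The documents do not show how a given wording is coded in MedDRA/J 20.1.

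**3. Whether another output supplies the missing patient count.**
- Table 5.1.1-1 gives patients and percentages at SOC level, but events at preferred-term level. The SOC row mixes low glucose with every other laboratory event. The preferred-term row counts events, with repeats of the same LLT in one patient counted once.
- The adverse drug reaction tables use the same layout, for events that meet the SAP's definition of a reaction.
- SAP 5.19.2 summarises lipids, renal, hepatic and pancreatic tests. Glucose is not among them.
- Fasting glucose appears in SAP 6.3 as an efficacy measure, with summary statistics and mean change in the Efficacy Analysis Set. There is no count of low values, and patients in the Other treatment group are excluded (SAP 2.0).
- SAP 1.1 mentions fasting glucose below 63 mg/dL, but only to exclude it from HOMA-β.

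The reader also cannot combine the tables. Suppose A patients have a listed term and the laboratory preferred term shows B events. The number of patients with either then lies anywhere from A (every laboratory case also has a listed term) to A + B (no overlap). With A = 40 and B = 10 the range is 40 to 50.

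**4. Illustration of size.** The planned N is 1,000 (Protocol 3.1). Two inputs are assumed because the documents give neither: p, the share of patients with any hypoglycaemia-type event, and f, the share of those reported only as a laboratory finding.

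Patients missed = N × p × f. Percentage shown = p × (1 − f).

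| p | f | Missed per 1,000 | Table shows |
|---|---|---|---|
| 1% | 10% | 1,000 × 0.01 × 0.10 = 1 | 0.90% |
| 1% | 50% | 1,000 × 0.01 × 0.50 = 5 | 0.50% |
| 5% | 5% | 1,000 × 0.05 × 0.05 = 2.5 | 4.75% |
| 5% | 20% | 1,000 × 0.05 × 0.20 = 10 | 4.0% |
| 10% | 5% | 1,000 × 0.10 × 0.05 = 5 | 9.5% |
| 10% | 20% | 1,000 × 0.10 × 0.20 = 20 | 8.0% |

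If no such event is reported, f = 0 and nothing is missed.

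**The case against.** The case for leaving the list alone is respectable. It is explicit, reproducible and unchanged across SAP versions. SAP 1.2 chooses scope risk by risk: acute pancreatitis uses a narrow query and hepatic impairment a broad one, so a specific clinical list for hypoglycaemia fits the pattern. Protocol 9.2.6 puts hypoglycaemia first among the events for which clinical course and diagnostic tests are sought, which should steer investigators towards naming it. An isolated low reading without symptoms is arguably not the same risk, and pooling it could inflate the rate. The event also remains visible in Table 5.1.1-1.

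Most of this stands. It is a good reason not to replace the ten-term definition. It does not answer the narrower point: the plan offers no patient count for the laboratory-coded events, and none can be derived from the tables it does offer. The SAP also gives no rationale for leaving them out.

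Some stronger readings are tempting but unsupported:
- A reader might infer that these events are lost from the survey. They are not; they are absent only from the hypoglycaemia rows.
- A reader might treat hypoglycaemia as the survey's key safety endpoint. The documents name no such endpoint; they call it an important identified risk.
- A reader might take the neonatal term as a sign of a careless list. Protocol Table 1 counts symptoms in breastfed infants as adverse events, so infant events are reportable.
- A reader might contrast the hyperuricaemia definition, which uses "Takeda MedDRA Query 20.1 (hereinafter, TMQ 20.1) (blood uric acid increased". That defines a concurrent disease, not an adverse-event risk, and only the query's name is visible.

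**Conclusion.** The point holds as a gap in presentation. Given the closed list and the separate laboratory blocks, a low glucose coded to a laboratory preferred term cannot reach the hypoglycaemia patient counts in Tables 5.1.3-1 and 5.1.3-2, and no other planned safety output gives the number of patients concerned.

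Its size is unknown. The 2.5 to 10 patients per 1,000 at 5% incidence rest wholly on assumed values of incidence and laboratory-only share, and on the view that such findings belong with hypoglycaemia. A reader might go further and infer a proven downward bias, or one that differs between treatment groups. The documents contain nothing on reporting habits by site or group, and SAP 5.1.3 is descriptive with no between-group test, so neither inference is supported.

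This is a modest improvement, worth making because it is cheap and leaves the existing result intact.

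**What to change.** Keep the ten-term definition in SAP 1.2 as the main hypoglycaemia line. In Tables 5.1.3-1 and 5.1.3-2 add two rows beneath it, for the total and for each treatment group:

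- (a) patients with an event coded to the laboratory preferred term or terms for decreased blood glucose, with name and code taken from MedDRA/J 20.1, the version the SAP already specifies;
- (b) patients with either a listed term or (a), each counted once.

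State in SAP 1.2 that the main line covers condition terms only and that the added rows show how far the count depends on that choice.

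The cost is a short SAP amendment, the added code or codes in the tabulation program and two rows per table. No new data are collected. The one drawback is that some laboratory-coded events may be asymptomatic; separate rows make this visible and leave the main line unchanged.

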1.3 Display digit

Term	Definition
Percentage (%)	
Percent of patients with adverse events or adverse drug reactions, etc. or percent of adverse events or adverse drug reactions, etc. :
 
Indicate to two decimal places rounded from three decimals.
 
Other than the above:
 
Indicate to one decimal place rounded from two decimals.

Summary statistics	
Mean, median, first quartile, and third quartile:
 
Indicate one lower digit rounded from two lower digits than the digit of the to-be evaluated data (refer to Section 1.6).
 
Standard deviation:
 
Indicate two lower digits rounded from three lower digits of the to-be evaluated data.
 
Minimum and maximum
 
Indicate the same digit number as that of the to-be evaluated data.

p-value	
Indicate to three decimal places rounded down from four decimals.
 
If the data is less than 0.001, display as $p < 0.001$.

1.4 Level of Significance and Confidence Coefficient

Two-sided 5%, two-sided 95%.

1.5 Handling of Laboratory/Measured Data

The evaluation time points for vital signs and laboratory tests will be at the start of Nesina treatment, 1 month, 3 months, 6 months, and 12 months after the start of Nesina treatment, and last evaluation.

The evaluation time points for electrocardiography, waist circumference, and coronary atherosclerosis and arteriosclerosis will be at the start of Nesina treatment, 12 months after the start of Nesina treatment, and last evaluation.

If multiple data exist within the relevant time point, calculate the absolute value of a difference in number of days from the reference number of days and select the minimum absolute value as the datum of the relevant evaluation time point. If the absolute values are same, select the datum at the latest examination/measurement day.

If "On treatment at 12 months after Nesina treatment" is selected in Section "Current Status of Nesina Treatment" in the survey sheet, all values will be used for analysis. If "On treatment at 12 months after Nesina treatment" is not selected, the values before the next day of the last administration of Nesina will be used for analysis.

The start day of Nesina treatment is defined as 0 days.

[Vital signs and laboratory test values]

Evaluation time point	Reference number of days	Lower limit of window	Upper limit of window
At start of Nesina treatment	0 days	30 days before Nesina treatment	Start day of Nesina treatment
1 month after start of Nesina treatment	30 days	1 day after start of Nesina treatment	60 days after start of Nesina treatment
3 months after start of Nesina treatment	90 days	61 days after start of Nesina treatment	136 days after start of Nesina treatment
6 months after start of Nesina treatment	180 days	137 days after start of Nesina treatment	273 days after start of Nesina treatment
12 months after start of Nesina treatment	360 days	274 days after start of Nesina treatment	456 days after start of Nesina treatment
At last evaluation	Select the latest datum from 1 to 456 days after the start of Nesina treatment		

[Electrocardiography and waist circumference]

Evaluation time point	Reference number of days	Lower limit of window	Upper limit of window
At start of Nesina treatment	0 days	30 days before Nesina treatment	Start day of Nesina treatment
12 months after start of Nesina treatment	360 days	1 day after start of Nesina treatment	456 days after start of Nesina treatment
At last evaluation	Select the latest datum from 1 to 456 days after the start of Nesina treatment		

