### 7.4 Creation and Submission of Survey Sheet

The Investigator will create the survey sheet for all enrolled participants and submit it to the Takeda around within 1 month after the end of the observation period. If Nesina administration cannot be confirmed, specify it (do not specify other columns).

For participants who early discontinue treatment with Nesina during the observation period for any reason, the Investigator will create the survey sheet for him/her and submit it to the Takeda around within 1 month after the end of necessary observation. However, for participants who early discontinue treatment with Nesina due to an adverse event, the Investigator will continue

observation even after treatment discontinuation, wherever possible, until the adverse event resolve or is resolving and will create the survey sheet and submit it to the Takeda.

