##### 2) Survey period

Each time point at the start of Nesina treatment, 1 month, 3 months, 6 months, and 12 months after the start of treatment (or treatment discontinuation)

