1.0 Definition of Terms and Handling of Laboratory/Measured Data

1.1 Definitions

Term	Definition
Nesina	Nesina tablet(s) is abbreviated as Nesina in this statistical analysis plan.
SOC	System Organ Class of MedDRA/J MedDRA/J version 20.1 is used for this document.
HLGT	High level group term of MedDRA/J
PT	Preferred term of MedDRA/J
LLT	Lowest level term of MedDRA/J
Registered patients	Patients whose registration was approved
Survey sheet collected patients	Patients whose survey sheets were collected
Survey sheet uncollected patients	Of the registered patients, patients whose survey sheets were uncollected.
Safety Analysis Set	Of the survey sheet collected patients, patients who were evaluated for safety analysis. For tabulation, the description of “total” means the Safety Analysis Set.
Not Safety Analysis Set	Of the survey sheet collected patients, patients who were excluded from safety analysis
Efficacy Analysis Set	Of the Safety Analysis Set, patients who were evaluated for efficacy analysis
Not Efficacy Analysis Set	Of the Safety Analysis Set, patients who were excluded from the efficacy analysis
First date of Nesina treatment	Of the start dates of the Nesina treatment period in patients, the earliest date is defined as the first date of Nesina treatment.
Last date of Nesina treatment	Of the last dates of the Nesina treatment in patients, the latest date is defined as the last date of Nesina treatment. If Nesina treatment is continued and the year, month, and date of the continued treatment period are specified, the year, month, and date of the continued treatment period are defined as the last date of Nesina treatment. If the data for the year, month, and date of the continued treatment period are missing, the following date is defined as the last date of Nesina treatment. (1) First date of Nesina treatment + 1 year (same month and date) for continued treatment of Nesina. (2) Latest date at which the following examinations/observations will be performed for the not-continued treatment of Nesina: 
 • [Date of examinations/ observations] 
 • Compliance with Nesina treatment

Term	Definition
	
 • Compliance with diet/exercise therapy • Laboratory tests • Body weight • Waist circumference • Pulse rate • Blood pressure • Electrocardiography • Tests for coronary atherosclerosis and arteriosclerosis

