5.19.2 Laboratory Values

(1) Patients to be tabulated and analyzed

Safety Analysis Set

(2) Details of tabulation and analysis

In laboratory values, summary statistics will be calculated for fasting triglyceride, total cholesterol, HDL-cholesterol, LDL-cholesterol, non-HDL cholesterol, serum creatinine, BUN, urinary albumin (corrected by creatinine), AST, ALT, γ -GTP, ALP, total bilirubin, amylase, lipase at each testing time point (start of Nesina treatment, 1 month, 3 months, 6 months, and 12 months after Nesina treatment and last evaluation). For changes from the start of Nesina treatment, summary statistics and the mean 95% confidence intervals will be calculated.

These laboratory values (mean and standard deviation) will be plotted. For the changes, the mean changes will be created using a bar graph.

Total patients and patients who are taking concomitant insulin preparation, rapid-acting insulin secretagogues, SGLT-2 inhibitors, or other drugs will be tabulated.

(3) Number of tables and figures

Table 5.19.2-1 and Figures 5.19.2-1 to 5.19.2-15

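### The SAP's last-dose cut-off also governs safety laboratory values and vital signs, so protocol-scheduled discontinuation results taken 2 or more days after a recorded last dose are left out of the 5.19.1 and 5.19.2 summaries

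*SAP*

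**What the plan says.** SAP 1.5 sets a single rule for laboratory and measured data. It opens with "The evaluation time points for vital signs and laboratory tests will be at the start of Nesina treatment", goes on to 1, 3, 6 and 12 months and last evaluation, and makes no distinction between efficacy and safety parameters. For patients marked as on treatment at 12 months, the rule ends "in the survey sheet, all values will be used for analysis". For all others, "the values before the next day of the last administration of Nesina will be used for analysis". Last evaluation is defined by "Select the latest datum from 1 to 456 days after the start of Nesina treatment", with no exemption from the cut-off. The cut-off wording is the same in all three SAP versions supplied.

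SAP 5.19.2 then summarises, in the Safety Analysis Set, a list that includes "serum creatinine, BUN, urinary albumin (corrected by creatinine), AST, ALT, γ -GTP, ALP, total bilirubin, amylase, lipase at each testing time point". SAP 5.19.1 does the same for pulse rate, blood pressure and weight.

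On collection, Protocol 9.2.5.1 and 9.2.5.2 run to "12 months after the start of treatment (or treatment discontinuation", and the Appendix schedule gives discontinuation its own column. None of these limits how many days after the last dose the discontinuation results may be taken. For patients who stop because of an adverse event, Protocol 7.4 asks for "observation even after treatment discontinuation, wherever possible, until the adverse event resolve or is resolving".

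SAP 1.1 covers a missing last treatment date. For patients who did not continue, the date becomes "Latest date at which the following examinations/observations will be performed for the not-continued treatment of Nesina".

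**The concern.** The protocol collects a scheduled set of safety measurements that the SAP may not use. A patient may stop at home and be seen some days later. That visit supplies the discontinuation panel, but it lies after the cut-off. The omission can affect only patients who stopped, and these include everyone who stopped for an adverse event. Hepatic impairment and acute pancreatitis are important identified risks in SAP 1.2, and AST, ALT, amylase and lipase are among the values affected. An on-treatment rule is easy to defend for HbA1c. The SAP gives no reason for extending it to safety laboratory data.

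**Working it through.** The plan states no figure that bears on this, so the check applies the rule to example patients and then compares the passages.

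**Inputs.** From SAP 1.5: start day = 0; windows of days 1–60 (1 month), 61–136 (3 months), 137–273 (6 months) and 274–456 (12 months); last evaluation = latest value in days 1–456. Let L be the day of the last dose and V the day of the visit, for a patient not on treatment at 12 months.

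**Two readings of the boundary.** Read strictly, a value is kept if V < L + 1. If the next day is meant to be included, it is kept if V ≤ L + 1.

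With L = 20, 100, 200 and 300, the result depends only on the gap V − L:

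| Days after last dose | Next day included | Strict |
|---|---|---|
| 0 | kept | kept |
| 1 | kept | dropped |
| 2 | dropped | dropped |
| 14 | dropped | dropped |
| 28 | dropped | dropped |

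Every dropped visit falls inside a nominal window. At a gap of 14 days, the visit days are 34 (1-month window), 114 (3-month), 214 (6-month) and 314 (12-month). With L = 100 and V = 114, the value lies in days 61–136 and in days 1–456, yet it enters neither the 3-month column nor last evaluation. If L = 10 and the first post-baseline panel is on day 14, then 14 > 10 + 1, and the patient contributes no post-baseline laboratory value.

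**Effect of a missing stop date.** Under SAP 1.1, L becomes the latest examination date, so no examination has V > L and nothing is cut. The same discontinuation result is thus used when the stop date is blank and left out when it is recorded.

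**Scale.** The documents give neither a discontinuation rate nor the interval between last dose and visit. With assumed rates only, and the planned 1,000 participants (Protocol 3.1):

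- Low: 10% stop and 25% of those are tested too late, so 1,000 × 0.10 × 0.25 = 25 patients.
- High: 30% stop and 75% of those are tested too late, so 1,000 × 0.30 × 0.75 = 225 patients.

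A ninefold range built on free assumptions is not an estimate. It shows only that the number need not be trivial.

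**The case against.** The case for leaving the rule alone is substantial.

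- **Design.** An on-treatment summary fits a survey whose laboratory schedule and adverse event period both end at 12 months or discontinuation. A result from the day of the last dose is kept. SAP 4.1.1 to 4.1.3 pair last evaluation with treatment discontinuation for compliance, which suggests that last evaluation is meant to stand in for the discontinuation column.
- **Other safety routes.** Protocol Table 1 counts an abnormal laboratory finding as a possible adverse event. SAP 5.1.1 to 5.1.3 tabulate adverse events and the important identified risks without applying the SAP 1.5 cut-off.
- **Nature of the tables.** SAP 5.19.1 and 5.19.2 are descriptive, single-arm summaries with no hypothesis test.
- **Protocol 7.4.** It concerns following an adverse event to resolution and does not itself schedule a laboratory panel.

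All of this limits the consequence, but it does not remove the omission. Last evaluation cannot stand in for discontinuation in a patient seen late, because the cut-off applies to it too. The scheduled discontinuation panel comes from Protocol 9.2.5.2 and the Appendix, so the point does not depend on 7.4.

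A reader might infer that the summaries are biased toward normal. The documents do not support that. An omitted value could be worse than the last on-treatment one, or it could already be recovering, since 7.4 follows events until they are resolving. A reader might also infer that safety signals are lost outright. An abnormality reported as an adverse event is still tabulated, and the omitted values are missing from the summaries, not from the collected data.

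**Conclusion.** The point holds as an inconsistency between what the protocol schedules and what the SAP analyses. Followed exactly, SAP 1.5 omits discontinuation laboratory values and vital signs from 5.19.1 and 5.19.2 whenever they were taken 2 or more days after a recorded last dose. Day-after values depend on how the sentence is read. The resulting incompleteness is confined to patients not on treatment at 12 months, and it varies with whether a stop date was recorded. This conclusion rests on the wording alone and assumes that last evaluation is subject to the cut-off, since no exemption is stated. The number of patients affected and the direction of any bias are unknown. The change is worth making because it is cheap and uses scheduled safety data. Nothing here invalidates the planned analyses.

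**What to change.** Keep the cut-off in SAP 1.5 for the Section 6 efficacy parameters and for the existing on-treatment time points. For 5.19.1 and 5.19.2, add treatment discontinuation as a separate tabulated time point that is not subject to the cut-off, and show the days since last dose. State explicitly whether a value from the day after the last dose is included.

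The discontinuation values should not be merged into last evaluation by allowing a fixed lag. The documents give no basis for choosing a lag, and a recovering off-drug value could then replace an abnormal on-treatment one.

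The cost is SAP wording, some programming and one extra column in the affected tables, with no new data collection. Some values in that column will reflect days off drug and should be labelled as such.
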